7.3.1.6.3 Tipping point analysis

This analysis will be implemented in three steps as described in Section 7.3.1.6.2.

The difference here is that, at the end of step 1, a “non-responder” status is imposed at Month 6 on withdrawals with an extra probability above that is modeled by the MAR assumption in the active treatment groups. Imputations under MAR in the placebo arm are not changed. This is implemented using the following example SAS[®] code:

```
data h4;
  set h3;
  * delta represents a probability of resetting imputed responder status to non-responder;
  delta = 0.05;
  call streaminit(1234);
  if m6_miss = "Y" and trt ne "Placebo" then do; * if responder status was missing (i.e.,
  imputed) and treatment group is not placebo;
    if rand("Uniform") < delta then m6 = 0;
  end;
run;
```

For example, if this probability is set to 10%, for every 10 subjects imputed as responders in the active treatment groups under the MAR assumption, 1 subject is randomly re-imputed as a non-responder. Note, that some subjects are of course imputed as non-responders directly under MAR.

To stress test the result from the main analysis, we impose a succession of probability adjustments starting at 5%, incrementing by 5% up to 100%.

7.3.1.6.4 Treatment effect over time

7.3.1.6.4.1 Variables

To assess the treatment effect over time on SRI-4, the composite endpoint SRI-4 response will be calculated as described in Section 7.3.1.2 for all post-baseline visits from Months 1 to 6.

7.3.1.6.4.2 Analysis

The analysis will be performed based on the same repeated measurements model as described in Section 7.3.1.5.

A figure presenting OR (95% CI) vs placebo over time will be produced.

7.3.1.7 Subgroup analyses

The same model as for the main analysis described in Section 7.3.1.5 will be fitted per subgroup.

A forest plot will be produced, displaying the OR for each dose vs placebo including 95% CIs at Month 6. The forest plot will include an ‘overall’ treatment effect, based on the secondary efficacy analysis and a reference line for no treatment effect at OR = 1.

For the analyses of the OCS and mSLEDAI-2K subgroups, the corresponding subgroup will not be included as a stratification factor in the model.

7.3.2 Response (no worsening) at Month 6 on BILAG-2004 disease activity index

7.3.2.1 Overview of analyses

The main estimator as well as sensitivity and supplementary estimators for the secondary estimand #2 as defined in Section 3.1.1 are summarized in Table 8.

Table 8 Overview of analyses for secondary estimand #2

Estimator	Section	Endpoint	Imputation method	Analysis
Main estimator	7.3.2.5	Response on BILAG-2004 at Month 6	None (MAR assumption)	Repeated measurements GLMM. To ensure that the estimand based on the treatment policy strategy can be estimated, the value for the variable of BILAG-2004 is used regardless of occurrence of intercurrent events, such as treatment discontinuation.
Sensitivity estimator #1	7.3.2.6.1	Response on BILAG-2004 at Month 6	None (MAR assumption)	Repeated measurements GLMM based on PPS
Sensitivity estimator #2	7.3.2.6.2	Response on BILAG-2004 at Month 6	MI assuming MAR	Repeated measurements GLMM on complete data imputed using MI assuming MAR
Sensitivity estimator #3	7.3.2.6.3	Response on BILAG-2004 at Month 6	MI assuming MNAR (tipping point)	Repeated measurements GLMM on complete data imputed using MI assuming MNAR
Supplementary estimator #1 (response over time)	7.3.2.6.4	Response on BILAG-2004 at Month 1, 2, 3, 4, 5 and 6	None (MAR assumption)	Repeated measurements GLMM.
Supplementary estimator #2 (subgroups)	7.3.2.7	Response on BILAG-2004 at Month 6	None (MAR assumption)	Subgroup analyses

BILAG-2004 = British Isles Lupus Assessment Group-2004; GLMM = generalized linear mixed model; MAR = missing at random; MI = multiple imputation; PPS = Per-Protocol Set.

7.3.2.2 Variables

The binary response variable of this endpoint is derived as described in Section 7.3.1.2 for the BILAG-2004 endpoint.

7.3.2.3 Handling of missing data

Missing data will not be imputed but will be handled by the repeated measurement's GLMM assuming that the data are MAR.

A summary table of the patterns of missingness from baseline up to Month 6 will be provided.

7.3.2.4 Hypothesis, statistical model and assumptions

The hypotheses for the secondary endpoint (response at Month 6 based on BILAG-2004) are presented in Section 7.1.1.

7.3.2.5 Analysis

The analysis will be performed based on the same repeated measurements model as described in Section 7.3.1.5.

Data of this endpoint will be summarized descriptively and listed using the FAS.

7.3.2.6 Supplementary/sensitivity analyses

7.3.2.6.1 Analyses based on PPS

The analysis of the secondary endpoint will be repeated using the PPS.

7.3.2.6.2 Multiple imputation under MAR

This analysis will be implemented as described in Section 7.3.1.6.2.

7.3.2.6.3 Tipping point analysis

This analysis will be implemented as described in Section 7.3.1.6.3.

7.3.2.6.4 Treatment effect over time

7.3.2.6.4.1 Variables

The same variable definitions as for the secondary endpoint are used. No imputation methods are applied. The endpoint is also derived for the time points Month 1 to Month 5.

7.3.2.6.4.2 Analysis

The repeated measurements analysis will be conducted in the same way as for the secondary endpoint described in Section 7.3.1.5.

A figure presenting OR (95% CI) vs placebo over time will be produced.

7.3.2.7 Subgroup analyses

Subgroup analyses will be conducted in the same way as defined for the secondary endpoint SRI-4.

7.4 Other efficacy endpoints analysis

No imputation methods are applied for the other efficacy endpoints. All other efficacy endpoints will be summarized descriptively and listed using the FAS. Additional analyses for the other efficacy endpoints are described in the sections below.

The time window approach, as defined in Section 5.4.4, is applied for the derivation of the following variables.

7.4.1 Response at Month 6 on the mSLEDAI-2K score

7.4.1.1 Variables

The binary response variable of this endpoint is derived as described in Section 7.3.1.2 for the mSLEDAI-2K endpoint.

7.4.1.2 Analysis

The analysis will be conducted in the same way as the analysis in Section 7.3.1.5.

7.4.2 Response (no worsening and improvement) at Month 6 on BILAG-2004 disease activity index

7.4.2.1 Variables

The composite endpoint (response at Month 6 based on the BILAG-2004 disease activity index) is a binary endpoint based on two variables, as defined below.

BILAG-1

A responder (1) is defined as having no new BILAG A organ domain score and at most one new BILAG B organ domain score assessed for the nine body systems. A responder can only be assessed if the full information of all body systems is available.

Non-responders (0) are defined as having one or more new BILAG A organ domain scores or at least two or more BILAG B organ domain scores. In the event of incomplete data in at least one of the body systems, but sufficient information to fulfill the non-response criteria, the subject is considered to be a non-responder.

Subjects that fit none of the above criteria are assigned a missing value.

BILAG-2

A responder (1) is defined as having an improvement of at least one BILAG A organ domain score to either B, C or D or as having an improvement of at least one BILAG B organ domain score to C or D. A responder can only be assessed if the full information of all body systems is available.

A non-responder (0) is defined as having no improvement in any BILAG A or BILAG B organ domain scores. In the event of incomplete data in at least one of the body systems, but sufficient information to fulfill the non-response criteria, the subject is considered to be a non-responder.

Subjects without any BILAG A or BILAG B organ domain scores at baseline are defined as responders.

Composite endpoint

A responder (1) for the endpoint response at Month 6 based on the BILAG-2004 scale (alternative definition) is defined as a responder of both variables, as defined above. If at least one of the two variables equal a non-response, the subject is considered to be a non-responder (0). In the event of at least one of the two variables being missing, the subject is assigned a missing value, unless it is clear that the subject is a non-responder.

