7 EFFICACY VARIABLES AND ANALYSES

7.1 Overview

The primary efficacy variable of the study is the absolute change of the mSLEDAI-2K score from baseline to Month 6. Changes for all time points from Month 1 through Month 6 will be derived and included in the statistical analysis model of the primary endpoint.

There are two secondary endpoints that are analyzed in hierarchical manner for each dose level comparison following any rejections of dose level comparisons hypotheses of the primary endpoint:

- Response at Month 6 on SRI-4 defined as follows:
 - Reduction from baseline of at least 4 points in the mSLEDAI-2Kand
 - No new BILAG A organ domain score and no more than one new BILAG B organ domain score compared with baselineand
 - No increase of more than 0.3 points on the PGA since baseline.
- Response (no worsening) at Month 6 on BILAG-2004 disease activity index defined as no new BILAG A organ domain score and no more than one new BILAG B organ domain score compared with baseline.

The other efficacy endpoints are described as follows:

- Response at Month 6 on the mSLEDAI-2K score defined as a reduction from baseline of at least 4 points.
- Response (no worsening and improvement) at Month 6 on BILAG-2004 disease activity index defined as follows:

- No new BILAG A organ domain score and no more than one new BILAG B organ domain score compared with baseline
- and
- Any BILAG A organ domain score at study baseline improved to B/C/D or any BILAG B organ domain score at study baseline improved to C/D.
- Response at Month 6 on SRI-5, -6, -7, -8 defined as the secondary endpoint (response at Month 6 on SRI-4) with reductions in mSLEDAI-2K of 5, 6, 7 and 8, instead of a reduction of 4.
 - Occurrence of mild, moderate and severe flares from baseline up to Month 6.
 - Time to first severe flare from baseline to Month 6 (severe flares defined as BILAG A organ domain score presence due to items that are new or worse).
 - Time to first flare from baseline to Month 6.
 - Change from baseline to Month 6 in PGA score.

Exploratory endpoints will be analyzed from baseline to a maximum of 12 months on all available assessments according to two groups:

- Group 1: All randomized subjects, for whom baseline is defined as the last available measurement before the start of randomized treatment in TP1.
- Group 2: Subjects re-randomized at Month 6, for whom baseline is defined as the last available measurement before the start of re-randomized treatment in TP2.

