7.4.3 Response at Month 6 on SRI-5, -6, -7, -8

7.4.3.1 Variables

The binary response variables of these endpoints are derived as described in Section 7.3.1.2 with a reduction in mSLEDAI-2K of 5, 6, 7 or 8, instead of a reduction of 4.

For SRI-X (X = 5, 6, 7 or 8) subjects with a baseline value of less than X will be excluded from the analysis.

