7.5.4.1 Variables

Group 1

The variable is derived as defined in Section 7.4.2 for each visit up to Month 12.

Group 2

The variable is derived as defined in Section 7.4.2 for each visit from Month 6 up to Month 12 based on the TP2 baseline value for all subjects in FAS-TP2.

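### SAP 7.4.2.1 credits BILAG improvement to subjects with no A or B at baseline, against the definition in SAP 7.1; response rates rise and the odds ratio can move toward 1

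*SAP*

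**What the plan says.** SAP 7.1 (Overview) gives the improvement limb as "Any BILAG A organ domain score at study baseline improved to B/C/D or any BILAG B organ domain score at study baseline improved" (to C or D). It repeats this for the exploratory version assessed at each visit.

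SAP 7.4.2.1 splits the endpoint into BILAG-1 (no worsening) and BILAG-2 (improvement). For BILAG-2 it says:

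- "A responder (1) is defined as having an improvement of at least one BILAG A organ domain score to either B, C or D", or at least one B to C or D.
- "A non-responder (0) is defined as having no improvement in any BILAG A or BILAG B organ domain scores".
- "Subjects without any BILAG A or BILAG B organ domain scores at baseline are defined as responders".

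A composite responder "is defined as a responder of both variables, as defined above", so BILAG-1 must also be met.

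SAP 7.4.3.1, on SRI-5 to SRI-8, handles subjects who cannot reach the threshold differently: "subjects with a baseline value of less than X will be excluded from the analysis".

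SAP 7.5.4.1 reuses the 7.4.2 derivation up to Month 12. For Group 2 it does so "for each visit from Month 6 up to Month 12 based on the TP2 baseline value".

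**The concern.** A subject with no A or B at baseline has nothing that can improve. Under SAP 7.1 this subject cannot respond. Under 7.4.2.1 the subject meets the BILAG-2 non-responder rule and, by the added sentence, is also a BILAG-2 responder. No rationale is given. A programmer working from 7.1 and one working from 7.4.2.1 would produce different response rates.

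For these subjects the composite is simply BILAG-1, the no-worsening response that SAP 7.3.2 already analyses as a secondary endpoint. The reported proportion therefore mixes improvement in some subjects with stability in others. The model cannot separate the two: SAP 7.4.2.2 points to the GLMM in 7.3.1.5, which has no term for baseline BILAG status, and the Group 2 model in 7.5.4.2 has none either.

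**Working it through.** The SAP states no response rate, effect size or share without A or B for this endpoint, so there is no planned figure to reproduce. What follows is an unadjusted illustration at one time point.

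**Notation.** f is the share with no A or B at baseline, taken as equal across arms. p is composite response in subjects with an A or B. q is the no-worsening rate in subjects without. T is cenerimod and C is placebo.

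**Three ways to score the same subjects**

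- SAP 7.4.2.1 rule: (1 − f)p + fq
- SAP 7.1 taken literally (non-response): (1 − f)p
- Exclusion: p, in a fraction 1 − f of the subjects

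**Risk differences that follow**

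- SAP rule minus non-responder scoring: f(qT − qC). This is zero when q is equal.
- SAP rule minus exclusion: f[(qT − qC) − (pT − pC)]. This is negative only when qT − qC is smaller than pT − pC.

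**Numbers.** All inputs are assumptions: pT = 50%, pC = 35%, q = 90% in both arms. Cells show cenerimod vs placebo, difference in points, and odds ratio.

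| f | SAP 7.4.2.1 rule | Non-responders | Excluded |
|---|---|---|---|
| 10% | 54.0 vs 40.5; 13.5; 1.72 | 45.0 vs 31.5; 13.5; 1.78 | 50 vs 35; 15; 1.86 |
| 20% | 58 vs 46; 12; 1.62 | 40 vs 28; 12; 1.71 | 50 vs 35; 15; 1.86 |
| 40% | 66 vs 57; 9; 1.46 | 30 vs 21; 9; 1.61 | 50 vs 35; 15; 1.86 |

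Worked line for f = 20%: 0.8 × 0.50 + 0.2 × 0.90 = 0.58 and 0.8 × 0.35 + 0.2 × 0.90 = 0.46. The odds ratio is (0.58/0.42)/(0.46/0.54) = 1.62.

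**In subjects.** SAP 2.1 gives 325/5 = 65 per arm. At f = 20% that is 13 subjects without A or B per arm, of whom 13 × 0.9 ≈ 12 would count as responders without any improvement.

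**When q differs by arm.** Take f = 20%, p = 50% vs 30%, and q = 90% vs 65%. The SAP rule gives 0.40 + 0.18 = 58% vs 0.24 + 0.13 = 37%, a difference of 21 points and an odds ratio of 2.35. Non-responder scoring gives 40% vs 24%, 16 points, 2.11. Exclusion gives 20 points, 2.33. There is no dilution against either alternative.

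**The case against.** The rule is explicit, prespecified and the same in every arm, and it sets only the BILAG-2 component, so no worsening is still required. The endpoint lies outside the Type I error strategy in SAP 7.1.1; the primary endpoint, SRI-4 and the secondary BILAG endpoint are untouched. All of this stands and limits the impact.

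Exclusion is not the SAP's general convention. It is stated for SRI-5 to SRI-8 only; SRI-4 and the 4-point mSLEDAI-2K response drop nobody with a baseline below 4. This also stands, so 7.4.3.1 is a precedent and does not bind. In Group 2, subjects with no A or B after six months on 4 mg are also of direct interest for the withdrawal objective in SAP 3.3, and dropping them would hide any loss of control.

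One might read 'any' in SAP 7.1 as 'every', so that a subject with no A or B meets the limb trivially. The 'at least one' wording in 7.4.2.1 rules that out.

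A reader might infer that the sentence necessarily dilutes the treatment difference, for instance from 15 points to 9 at f = 40%. The documents do not support that. The 15 points belong to the subset with an A or B; SAP 7.1 taken literally also gives 9. A reader might also infer that response in Group 2 is largely automatic. That needs a high share without A or B at the TP2 baseline and a high no-worsening rate, and the SAP gives neither.

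**Conclusion.** Wrong as written, with low impact. The contradiction is established from the text alone and needs no assumption. The rise of f × q in each arm, relative to SAP 7.1, is arithmetic and is zero if no such subjects are enrolled.

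Movement of the odds ratio toward 1 is possible but conditional. Under the tabulated assumptions at f = 20% the sentence itself accounts for 1.71 to 1.62; the larger gap, from 1.86, is against exclusion. A smaller risk difference is not shown against SAP 7.1 scoring when q is equal, and a sufficiently favourable q for cenerimod removes the dilution.

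The entry criteria are not in the supplied text, so f at study baseline cannot be bounded and may be small. That f is larger at the TP2 baseline is a reasonable inference after six months on 4 mg, but no more than that.

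**What to change.** 1. Remove the sentence from SAP 7.4.2.1, and state in 7.1, 7.4.2.1 and 7.5.4 that the improvement endpoint is analysed in subjects with at least one BILAG A or B at the relevant baseline. Deleting the sentence alone would leave the others as non-responders by default.
2. Report the number without A or B by arm, at the study baseline and at the TP2 baseline.
3. Show scoring these subjects as non-responders as a sensitivity analysis.
4. For Group 2, keep subjects without A or B visible through a no-worsening summary by re-randomized arm.

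The cost is a wording change, one filter and a few outputs. The filter uses only baseline data, so the randomized comparison within the subset is preserved. The downside is a smaller n: at an assumed f = 20%, 65 × 0.8 = 52 per arm in TP1. In Group 2, with at most about 65/2 ≈ 32 per arm, an assumed f = 40% would leave about 32.5 × 0.6 ≈ 19 to 20. If the results concerned are already unblinded, keep the prespecified rule visible and label the restricted analysis as added.

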7.4.2.2 Analysis

The analysis will be conducted in the same way as the analysis in Section 7.3.1.5.

7.4.3 Response at Month 6 on SRI-5, -6, -7, -8

7.4.3.1 Variables

The binary response variables of these endpoints are derived as described in Section 7.3.1.2 with a reduction in mSLEDAI-2K of 5, 6, 7 or 8, instead of a reduction of 4.

For SRI-X (X = 5, 6, 7 or 8) subjects with a baseline value of less than X will be excluded from the analysis.

7.4.3.2 Analysis

The analysis will be conducted in the same way as the analysis in Section 7.3.1.5.

7.4.4 Occurrence of mild/moderate and severe flares from baseline up to Month 6

7.4.4.1 Variables

Derived data for this endpoint is provided by an external vendor. Data is categorized into mild/moderate or severe flares.

The definition of flares is provided in appendix 12 of the protocol [D-22.031].

7.4.4.2 Analysis

The number and percentage of subjects with no flare, mild/moderate flare and severe flare from baseline up to Month 6 overall as well as at every visit will be summarized by treatment group.

7.4.5 Time to first severe flare up to Month 6

7.4.5.1 Variables

The time to first severe flare during TP1, from baseline to Month 6 visit (in days) is defined as:

[Date of first severe flare – Date of treatment start date + 1] in days.

The start date of the first severe flare must be within TP1. Missing dates are imputed as follows:

- Day missing: Impute first day of the month or if earlier than first study drug intake, impute day of first study drug intake.
- Day and month missing: If the year is in the interval of (First study drug intake; Month 6) impute the first study drug intake date, otherwise keep as missing.
- If the date is completely missing, then include severe flare in the analysis and set the date to the first study drug intake date.

For subjects without any severe flares, the time to the first severe flare is censored at the Month 6 visit date or at the time of last available observation without any severe flares in TP1 if the subject discontinues study prior to Month 6.

Subjects with a severe flare during TP1 are considered as having an event ('1'), censored subjects as having no event ('0').

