2.3.2 Treatment periods

The study comprises 2 treatment periods: TP1 and TP2.

TP1 lasts for 6 months. It starts with the administration of the first dose of study treatment, after subject randomization, and ends at the Month 6 visit.

Starting at the Month 6 visit, TP2 lasts for up to 6 months and ends at the Month 12 visit.

If a randomized subject discontinues treatment prematurely in TP1 or TP2, the subject will have a premature EOT visit, stay in the study, and complete all protocol-mandated visits up to the Month 12 visit (unless the subject withdraws consent earlier).

At the time of the Month 12 visit, the EOT visit will take place.

Furthermore, at this time the EOS visit will take place for subjects with premature EOT occurring at least 6 months prior to the Month 12 visit. For subjects with premature EOT occurring less than 6 months prior to the Month 12 visit, the 6-month FU period must be completed in its entirety. For example, if a subject has premature EOT at Month 8 occurring four months prior to the Month 12 visit, Month 9, Month 10, Month 11 and Month 12 visits, also functioning as FU1, FU2, FU3, and FU3a, are conducted as planned, along with FU3b and EOS visits after the Month 12 visit. This completes 6 months of follow-up.

[figure not shown]

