5.4 Analysis periods

5.4.1 Efficacy observation period

Efficacy observation periods are defined as:

- TP1: From treatment start date (TP1) to the date of last visit performed in TP1 (up to Month 6);
- TP2: From treatment start date (TP2) to the date of last visit performed in TP2 (up to Month 12). This period is defined for all re-randomized subjects;
- Pooled TP1/TP2: From treatment start date (TP1) to the date of last visit performed in TP1/TP2 (up to Month 12).

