6.8.3.5 British Isles Lupus Assessment Group

6.8.3.5.1 Variables

Data is taken from the derived BILAG-2004 screening summary eCRF page BILAG-2004 Grading. The data is received from an external vendor.

For each of the nine assessed BILAG-2004 categories gradings are displayed in 6 categories (A, B, C, D, E, not gradable).

6.8.3.5.2 *Analysis*

For each of the 9 subcategories descriptive summary statistics will be produced using the FAS, by treatment group and overall.

Data will also be listed using the SCR.

6.8.3.6 *SELENA flare index*

6.8.3.6.1 *Variables*

Data is taken from the SELENA Flare Index eCRF pages which are aggregated and provided by an external vendor.

Data are categorized into the following flare categories:

- No flare
- Mild or moderate flare
- Severe flare

6.8.3.6.2 *Analysis*

Flare data will be summarized using descriptive statistics using the FAS.

Summary tables will be presented by treatment group and overall.

Flare data will be listed using the SCR.

6.8.4 **Other baseline characteristics**

6.8.4.1 *Discharge from medical monitoring on day of first study drug intake*

Subjects fulfilling the discharge criteria at 6 hours on the day of first study drug intake may leave the hospital.

Subjects not fulfilling the discharge criteria at 6 hours will stay in hospital until the discharge criteria are fulfilled. The discharge criteria are checked every hour up to 12 hours. If the discharge criteria are not met after 12 hours, the subject will be permanently discontinued from study treatment.

Discharge information is taken from the eCRF pages “Discharge from Medical Monitoring - 6 hours” and “Discharge from Medical Monitoring - 12 hours”.

6.8.4.1.1 *Variables*

The number of subjects being discharged at 6 hours, between 6 and 12 hours and the number of subjects being discontinued after 12 hours of medical monitoring are derived on the day of first study drug intake.

For subjects that needed to stay longer than 6 hours, the time leaving the hospital is categorized hourly.

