7.5.8.1 Variables

Group 1

The variable is derived as defined in Section [7.4.5.1](#), for visits up to EOT (including TP2) and up to Month 12.

Group 2

The variable is derived as defined in Section [7.4.5.1](#), from the Month 6 visit up to EOT and up to Month 12 for all subjects in FAS-TP2. The censoring is derived from start of TP2, instead of start of TP1.

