8.2.1 Variables

AEs are classified as ‘Treatment-emergent AEs’ if the start date of the AE is on or after the date of first study drug intake (by time and date) up to EOT + 180 days (inclusive).

AEs with onset during TP1 are defined in the interval:

[First study drug intake (by time and date); Month 6 visit or EOT
(if EOT date is on or before Month 6 visit date)]

AEs with onset during TP2 are defined in the interval:

[Month 6 visit + 1 day; EOT].

Any AE prior to start of treatment (by time and date) in TP1 and AEs 121 days or more after EOT are considered non-treatment-emergent AEs.

TEAEs on Day 1 are reported up to 24 hours after first study drug intake in TP1 and on or after the time of first study drug intake.

TEAEs on the day of re-initiation are defined in the same way, but for the day of the re-initiation.

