12 APPENDICES

12.1 Visit and assessment schedule

PERIODS	Name	SCREENING	TREATMENT PERIOD 1							
	Duration	Up to 60 days	From Day 1 to Month 6							
VISITS	Number	1	2	2a	3	4	5	6	7	8
	Name	Screening	Randomization ⁽¹⁾		Month 1	Month 2	Month 3	Month 4	Month 5	Month 6
	Time	Day -60 to Day -1	Day 1	Day 2	Day 30 (±2 days)	Day 60 (±7 days)	Day 90 (±7 days)	Day 120 (±7 days)	Day 150 (±7 days)	Day 180 (±7 days)
Informed consent		X								
Inclusion/exclusion criteria		X	X							
Demographics		X								
Smoking and alcohol consumption status		X								
Medical history and SLE history		X								
SLE and previous/concomitant therapies		X	X		X	X	X	X	X	X
Physical examination ⁽²⁾		X	X		X	X	X	X	X	X
Body weight and height ⁽³⁾		X								
mSLEDAI-2K, BILAG, PGA, SFI		X	X		X	X	X	X	X	X
FACIT-Fatigue, PGIS-F			X				X			X
PGIC-F							X			X
SF-36v2™ and Lupus QoL			X							X
Chest X-ray ⁽⁵⁾		X								
Vital signs: SBP/DBP* ^{(6) (7)}		X	X		X	X	X	X	X	X
12-lead ECG* ⁽⁷⁾		X	X				X			X
ECG Holter* ⁽⁸⁾			X	X						
Echocardiography ⁽⁴⁾		X								X
Spirometry*		X					X			X
Ophthalmological examinations		X					X			X
OCT		X					X			

PERIODS	Name	SCREENING	TREATMENT PERIOD 1							
	Duration	Up to 60 days	From Day 1 to Month 6							
VISITS	Number	1	2	2a	3	4	5	6	7	8
	Name	Screening	Randomization ⁽¹⁾		Month 1	Month 2	Month 3	Month 4	Month 5	Month 6
	Time	Day -60 to Day -1	Day 1	Day 2	Day 30 (±2 days)	Day 60 (±7 days)	Day 90 (±7 days)	Day 120 (±7 days)	Day 150 (±7 days)	Day 180 (±7 days)
PK sampling* ⁽⁹⁾			X		X	X	X			X
Hematology and blood chemistry* ⁽¹⁰⁾		X	X		X	X	X	X	X	X
Pregnancy test ⁽¹¹⁾		X	X		X	X	X	X	X	X
Viral serology / TB test		X								
Additional sample for virology			X							
SLE biomarkers		X	X ⁽¹³⁾		X	X	X ⁽¹³⁾	X	X	X ⁽¹³⁾
Urine protein-to-creatinine ratio		X	X		X	X	X	X	X	X
Urinalysis (dipstick)		X	X		X	X	X	X	X	X
Study treatment dispensing/return and accountability			X		X	X	X	X	X	X
AEs ⁽¹²⁾ / SAEs ⁽¹²⁾		X	X		X	X	X	X	X	X

PERIODS	Name	TREATMENT PERIOD 2					
	Duration	From Month 6 up to Month 12					
VISITS	Number	9	10	11	12	13	14
	Name	Month 7	Month 8	Month 9	Month 10	Month 11	Month 12 / End-of-Treatment (EOT) / premature discontinuation of study treatment (pEOT) ⁽¹⁴⁾
	Time	Day 210 (±7 days)	Day 240 (±7 days)	Day 270 (±7 days)	Day 300 (±7 days)	Day 330 (±7 days)	
SLE and previous/concomitant therapies		X	X	X	X	X	X
Physical examination ⁽²⁾		X	X	X	X	X	X
Body weight ⁽³⁾							X
mSLEDAI-2K, BILAG, PGA, SFI		X	X	X	X	X	X

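### Group 2's time-to-flare window opens at the visit that normally supplies the TP2 baseline, and for TP1 the SAP contradicts itself on whether pre-dose Day 1 flares are events

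*SAP*

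**What the plan says.** **Event definition.** SAP 7.4.5.1 defines time to first severe flare as "Date of first severe flare – Date of treatment start date + 1] in days", with the condition "The start date of the first severe flare must be within TP1". Section 7.4.6.1 reuses this for any flare. A flare with a completely missing date is kept and given the first-dose date. One with only the day missing is moved up to the first-dose date if the first of that month is earlier.

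**What TP1 is.** Section 2.3.2 says of TP1: "It starts with the administration of the first dose of study treatment, after subject randomization, and ends at the Month 6 visit". Section 2.3.1 ends Screening on the Randomization day, before the first intake. Section 5.4.1, which defines the efficacy observation period, starts from a date instead: "TP1: From treatment start date (TP1) to the date of last visit performed in TP1 (up to Month 6".

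**When flares are scored.** The schedule in 12.1 marks "mSLEDAI-2K, BILAG, PGA, SFI" at Screening, Randomization (Day 1) and each month. Section 6.8.3.6 reports the SELENA flare index as a baseline characteristic, in three categories from no flare to severe flare.

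**Group 2.** Section 7.5.8.1 derives the variable "from the Month 6 visit up to EOT and up to Month 12 for all subjects in FAS-TP2"; 7.5.9.1 also starts at that visit. Section 5.2 defines the TP2 baseline as the last value up to and including the day of re-randomization.

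**Adverse events, for contrast.** Section 8.2.1 assigns TP1 onset by date and clock time, and starts TP2 onset on the day after the Month 6 visit.

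**The concern.** A time-to-event comparison should count only events that can follow the treatment being compared. In Group 2 that treatment starts after the Month 6 assessment, yet the event window opens at that assessment. A flare scored there arose on 4 mg, before the switch to 2 mg or placebo. Such flares fall equally on the two re-randomized arms in expectation. They add events that carry no treatment information and remove those subjects from the later risk set, so a true HR other than 1 is estimated closer to 1, and the Kaplan-Meier estimate gets an early step that is not a treatment effect.

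For TP1 the same would happen to flares scored before the first dose on Day 1, if they are counted. The text does not settle whether they are, so two programmers could derive different event counts from it.

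**Working it through.** **1. Day count.** A flare dated on the first-dose date has time 0 + 1 = day 1. It is a valid event if TP1 is read by date. A flare with no date also becomes a day-1 event, by rule.

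**2. TP1: passages side by side.**
- Towards inclusion: 5.4.1 (starts at a date) and the formula in 7.4.5.1 (dates only, no clock time).
- Towards exclusion: 2.3.1 and 2.3.2 (pre-dose Day 1 is Screening). Section 7.4 says the time windows apply to its variables, and Table 4 places Day 1 in Baseline and starts Month 1 on day 2.
- Open: 7.4.5.1 speaks of a start date that can be partial, which suits an onset date. Section 7.1 defines flares by new or worse organ-domain scores, in one place against the previous visit, which suits a visit date. Protocol appendix 12, which holds the flare definition, is not among the documents supplied.

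**3. Group 2: passages side by side.** The window starts at the Month 6 visit (7.5.8.1, 7.5.9.1), and that visit normally supplies the TP2 baseline (5.2). Table 4 does not help, because days 166 to 195 are labelled Month 6, not Baseline. The Group 2 repeated-measures models (7.5.2.2 to 7.5.6.2) use only Months 7 to 12. The Cox models in 7.5.8.2 and 7.5.9.2 have no such restriction.

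**4. Size, as illustration.** The plan gives no flare rate, HR or power for these endpoints, so there is no figure to reproduce.
- From the SAP (2.1): 325 / 5 = 65 per arm in TP1; at most 65 / 2 = 32.5 per arm in Group 2.
- Assumed: q, the share of each arm with a flare at the baseline assessment; p, the six-month placebo risk among the rest; and the true HR.
- Expected events per pair of arms: n × {2q + (1 − q)[p + 1 − (1 − p)^HR]}. With n = 65, q = 0.05, p = 0.20, HR = 0.50: 65 × [0.10 + 0.95 × (0.20 + 0.1056)] = 25.4.
- Estimated HR: root of the large-sample Cox score equation, with ties broken as continuous time, as under the exact-ties option in the SAP code. Hand check: weight the log HR by event share. Early events are 0.10 / 0.390 = 26% of the total, and exp(0.74 × ln 0.50) = 0.60.
- Power: Φ(|ln HR| × √events / 2 − 1.96).

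For p = 20% and true HR 0.50:

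| q | HR | Events, 65/arm | Power | Events, 32.5/arm | Power |
|---|---|---|---|---|---|
| 0 | 0.50 | 19.9 | 34% | 9.9 | 19% |
| 2% | 0.55 | 22.1 | 30% | 11.0 | 17% |
| 5% | 0.60 | 25.4 | 25% | 12.7 | 15% |
| 10% | 0.68 | 30.9 | 19% | 15.4 | 12% |

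At q = 5% the HR is 0.67 if p is 10%, and 0.55 if p is 40%. With true HR 0.70 and p = 20%, q = 5% gives 0.76. With true HR 1 it stays 1.00 at both values tried, q = 5% and 20%.

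**The case against.** The strongest case against is on Day 1. A reader might infer that the SAP does count flares scored at Randomization as day-1 events. The documents do not support that. On the definition in 2.3.2 the entry condition itself shuts them out, and Table 4 points the same way. Section 6.8.3.6 treats flares of that kind as baseline status. If the vendor supplies an onset date, a flare seen at Randomization that began earlier predates treatment. All of this stands, so for TP1 the finding is an unresolved contradiction, not a rule that miscounts. The undated-flare rule creates day-1 events on either reading, but applies only to flares with no date.

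For Group 2 it can be said that 5.4.1 starts the TP2 efficacy period at the TP2 treatment start date. That does not repair the specific wording of 7.5.8.1 and 7.5.9.1, and it works by date, so it would still admit the Month 6 assessment if TP2 dosing began that day. A reader might also call it double counting that the same flare falls in TP1. That is not an error in itself: the TP1 and Group 2 models are separate and have different baselines.

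It is also fair that little rests on these analyses. They are other or exploratory endpoints outside the hierarchy in 7.1.1, and the log-rank test has been removed. That limits the consequence but does not remove the reason to fix the definition.

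**Conclusion.** The Group 2 point holds on the text as written. The window includes the assessment that normally serves as the TP2 baseline, so flares from time on 4 mg count as post-switch events and bias the 2 mg versus placebo HR towards 1 when there is a true effect. The TP1 point holds as an inconsistency: 5.4.1 and 7.4.5.1 against 2.3.1, 2.3.2 and Table 4, with the meaning of the flare date unstated.

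The direction rests on early flares being equally likely in the compared arms, which randomization and re-randomization provide in expectation. The size is unknown. The HR and power figures above should not be read as the expected loss in this trial, because the prevalence, risk and effect behind them are all assumed. If there is no treatment effect, there is no bias. No confirmatory claim is affected. The change is still worth making, since it is nearly free and removes events that precede the treatment under study.

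**What to change.** - In 7.4.5.1, and so 7.4.6.1: count only flares scored at an assessment made after first study drug intake by date and time, that is from the Month 1 window onward. Treat flares scored at Screening or before the first dose on Day 1 as baseline status.
- Align the start of TP1 in 5.4.1 with 2.3.2.
- State whether the flare date is the onset date or the visit date.
- In 7.5.8.1 and 7.5.9.1: start the event window after the first TP2 dose, or on the day after the Month 6 visit as for adverse events.
- In 7.4.4.2: start the overall flare count at the first post-baseline visit.

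The cost is SAP wording and a small change to the derivation; no new data are needed. The downside is slightly fewer events.
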